1. PURPOSE OF THE STUDY

a. Brief Summary

Intermittent theta-burst stimulation (iTBS) is a patterned form of repetitive transcranial magnetic stimulation (rTMS), an effective, neuromodulatory treatment for refractory major depressive disorder (MDD). Accelerated rTMS paradigms have become of increasing clinical interest to address the potential limiting factors of dose response variability and the burden in weeks of treatment at great financial expense. Even with reduced treatment time in iTBS compared with standard rTMS (10 mins vs the traditional 40 minutes, respectively), there remains a barrier in requiring weeks or months of daily treatment sessions for desired response. Our recent pilot data (IRB33797) assessing the safety, tolerability, and efficacy of an accelerated iTBS protocol has shown a 90% antidepressant response in individuals with treatment resistant MDD, over the course of only 5 days. (Cole et al. American Journal of Psychiatry, 2020).

This study intends to utilize our novel accelerated iTBS (aiTBS) treatment approach, titled Stanford Accelerated Intelligent Neuromodulation Therapy (SAINT) for symptoms of bipolar treatment resistant depression (TRD), while assessing changes in neuroimaging biomarkers.

b. Objectives

1. To determine if bilateral, accelerated intermittent theta-burst stimulation (aiTBS) can provide a rapid reduction in depressive symptoms among a group of individuals with bipolar depression, that is equivalent to the efficacy of the traditional repetitive transcranial magnetic stimulation (rTMS) paradigm for unipolar depression.
2. To determine if responders to this protocol will have a similar change in functional connectivity between the left DLPFC and subgenual anterior cingulate cortex (sgACC) after treatment.

3. To determine whether similar covariates may operate as potential predictors of antidepressant treatment response and durability (time to relapse) in bipolar depression.

c. Rationale for Research in Humans

All transcranial magnetic stimulation treatment studies must be conducted in humans.

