2. STUDY PROCEDURES

a. Procedures

We will recruit a total of 30 outpatient participants for an open label pilot study (aged 18-80 years old) using intermittent theta burst stimulation (iTBS) over the left dorsolateral prefrontal cortex (LDLPFC) and right dorsolateral prefrontal cortex (RDLPFC) (up to five days, up to 10x/day) with the MagPro rTMS System. Participants will be required to meet diagnostic criteria for Bipolar I or Bipolar II (without psychosis or rapid cycling), in a current depressive episode. History related to participant's mood cycle will be obtained to ensure treatment is delivered during a depressive cycle which will be expected to span beyond the length of the 5-day treatment period based on the participant's most recent depressive episode duration. Psychiatric history will be obtained through each participant's psychiatric provider records to confirm diagnosis and bipolar symptom cycle history, which will be reviewed and confirmed during screening.

Participants will be excluded if they have been hospitalized within the last 6 months due to suicidality, depression severity or hypomania.

Participants will be required to have stabilized on medications (including at least one of the following as a mood stabilizer Lithium with a level of at least 0.6, Depakote with a level of at least 50, or a therapeutic dose of carbamazepine, oxcarbamazepine, or an antipsychotic) without dose changes for at least 6 weeks prior to the active study time period.

They will be ruled out if they have had a manic episode in the past year or a hypomanic episode in the last 6 months.

Participants will be asked to stay on their psychotropic medications for stabilization throughout the screening, baseline, and active study time periods. Participants will be required to have an established psychiatric prescriber.

We will use an adapted baseline covariate of the Maudsley Staging Method for TRD bipolar depression.

The study will have 4 time-periods:

- screening time period
- baseline time period
- active study time period

- follow-up time period

We will utilize a modified study design version of Williams (2018) and Cole et al (2020)

Reference: Cole EJ, Stimpson KH, Bentzley BS, et al. Stanford Accelerated Intelligent Neuromodulation Therapy for Treatment Resistant Depression. Am J Psychiatry. 2020;177(8):716-726.

doi:10.1176/appi.ajp.2019.19070720

Study Visit Schedule

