Pre-screening	Screening Visit 1 Remote	Baseline visit2	Day1-5 Visit 3-7	Immediate Post) (Tuesday-Wednesday) Visit 8	Self-reports (Post 2,3week)	Post 4 week Visit 10 Remote visit (optional) Self-report(requirement)
Consent						
Initial screen consent	Screening consent	Study consent form Capacity consent				
Clinician Administered Assessments / Scales						
Demographic	Stanford demo					
Demographic II	inclusion/exclusion					
Dx - Psychiatrist - Tx Hx	MRI safety TASS (TMS safety) BSL- 23(borderline)	MT	aTBS checklist			
Med & Psych Hx	Med Med & Psych	Self-report Mx review	Concomitant Mx review			

	Hx ATHF-current ATHF-lifetime	Concomitant Mx review				
Depression Sx - IDS-SR	Mausley+Thase Rush		randomization			
Mania Sx - Past - Current - Med	SCID-including BPD module MINI					
Psychotic Sx - Lifetime		UTox UPreg	UTox	UTox		
		COVID-19 screening	COVID-19 screening	COVID-19 screening		
Self-questionnaire						
	MADRS-S GAD-7	MADRS-S PHQ-8 GAD-7 BSS	MADRS-S-24h PHQ-8 BSS	PHQ-8 MADRS-S GAD-7 BSS	PHQ-8 (2,3w)	PHQ-8 MADRS-S GAD-7
Clinician rating						
Scanning safety	MADRS-C HAMD-17	MADRS-C HAMD-17	HAMD-6 YMRS	YMRS MADRS-C		MADRS-C HAMD-17

	YMRS	YMRS		HAMD-17		YMRS
Mx						
- MS	CSSRS	MSSI		MSSI		MSSI
- SSRI	MSSI					
- SNRI						
- TCA						
- MAOi						
- APx						
- AED						
- Thyroid						
- BB						
- Amphetamine						
- MPH						
- Nonstimulant						
- Antianxiety						
- Insomnia						
- other						
		CGI-S		CGI-S		CGI-S
				CGI-I		CGI-I
OTHER Self reports						
	Holmes & Rahe Stress					
	PSQI					
	SHAPS	SHAPS		SHAPS		SHAPS
		CTQ				

		Self-criticism scale					
Other measure							
		Resting EEG		Resting EEG			
			Adverse events				
			HRV				
		Resting state fMRI connectivity		Resting state fMRI connectivity			
		T1 anatomical		T1 anatomical			
		DWI		DWI			

b. Procedure Risks

These methods are the least risky because the intervals of stimulation have been shown to be appropriate for theta burst stimulation in the motor system with no adverse outcomes. The addition of R-DLPFC iTBS should provide an additional safety measure for the risk of hypomanic/manic conversion, although this risk is low. Additionally, all speech samples used for analyses will be based on randomly segmented splices of audiotapes; further, the 5-minute speech sample requires participants to answer a set of standardized questions without any reference to personal information.

c. Use of Deception in the Study

No deception will be used.

d. Use of Audio and Video Recordings

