5. PARTICIPANT POPULATION

a. Planned Enrollment

- b. We will recruit a total of 30 outpatient participants for an open-label pilot study (aged 18-80 yo) using bilateral intermittent theta burst stimulation (iTBS) over the left dorsolateral prefrontal cortex (LDLPFC) and right dorsolateral prefrontal cortex (RDLPFC) (five days, 10x/day) with the MagPro rTMS System.

c. Age, Gender, and Ethnic Background

We will recruit 30 participants ages 18-80, all gender and ethnic backgrounds.

d. Vulnerable Populations

The patient population will not include children or pregnant women as these individuals will not be candidates for psychiatric interventions. The sample will include economically/educationally disadvantaged as long as they have a fixed phone number by which to be contacted. Employees and students will be included as long as they are not lab members (due to HIPAA).

e. Rationale for Exclusion of Certain Populations

Women and minorities are included. Children are not included because they are typically excluded from psychiatric interventions e.g., aTBS and children will not be clinical staff numbers.

f. Stanford Populations

N/A

g. Healthy Volunteers

N/A

h. Recruitment Details

Patients will be recruited through the outpatient clinic in the psychiatry department, through a database of potential research subjects that have consented to contact for future research through the depression research clinic and through physician referral. Patients will either directly contact the research team for study participation, or they will give consent to the referring physician and the physician will communicate directly with the study team.

We have a bipolar pre-screening REDCAP database which we will use to screen eligibility.

We will also use the Stanford Research Registry (protocol 25422) to recruit study participants. The research registry is a list of individuals who have consented to be contacted by researchers at Stanford and at present includes over 1,000 volunteers.

For participants who participate in studies IRB 33797 and IRB 37224, data will be shared with studies IRB 33797 and IRB 37224.

Social media platforms such as Facebook will be used, as well as Craigslist. Flyers and brochures will be used to recruit as well.

i. Eligibility Criteria

i. Inclusion Criteria

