1. Participants aged 18yo-80yo with a primary diagnosis of bipolar I or II disorder in a current major depressive episode or bipolar affective disorder II in a current major depressive episode.
2. Able to read, understand, and provide written, dated informed consent prior to screening. Participants will be deemed likely to comply with study protocol and communicate with study personnel about adverse events and other clinically important information.
3. Currently diagnosed with Bipolar Depression, according to the criteria defined in the Diagnosis and Statistical Manual of Mental Disorders, Fourth Edition, Text Revision (DSM-IV-TR)
4. Meet the threshold on the total HAMD17 score of $>/=20$ at screening/baseline.
5. Not in a current state of mania (Young Mania Rating Scale) or psychosis (MINI)
6. In good general health, as ascertained by medical history.
7. Access to clinical rTMS after trial completion
8. Must have a stable psychiatrist during study enrollment, who confirms diagnosis of BPD I or II.
9. Must be on a mood stabilizer regimen for 6 weeks prior to study enrollment and agree to continue this regimen during study period
10. Meet the threshold on the MADRS, with a total score of $>/=20$ at screening/baseline.
11. History of ECT intolerance or exposure is permitted.
12. If traveling from out of town for the study, participants will need to have a companion with whom they're staying with while receiving open-label treatment.

ii. Exclusion Criteria

1. Any structural lesion e.g., structural neurological condition, more subcortical lesions than would be expected for age, stroke effecting stimulated area or connected areas or any other clinically significant abnormality that might affect safety, study participation, or confound interpretation of study results.
2. Metal implant in brain (e.g., deep brain stimulation), cardiac pacemaker, or cochlear implants
3. History of epilepsy/ seizures (including history of withdrawal/ provoked seizures)
4. Shrapnel or any ferromagnetic item in the head
5. Pregnancy
6. Autism Spectrum disorder
7. Any current or past history of any physical condition which in the investigator's opinion might put the subject at risk or interfere with study results interpretation
8. Active substance abuse (<1 week) or intoxication verified by toxicology screen-- of cocaine, amphetamines, benzodiazepines
9. Cognitive impairment (including dementia)

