If the participant displays an increased YMRS score (>=2 points) on 2 questions, stimulation will be switched to all right sided treatment to prevent any possibility of further inducing hypomania or mania. If these symptoms persist or increase to any greater degree during that same treatment series, the patient will be treated with Ativan and their primary psychiatrist will be contacted by the PI. If any of the research team or clinical staff believe that the participant may be showing signs of hypomania/mania, the YMRS will be administered by trained personnel immediately, the researchers will not wait until the daily assessments are conducted.

d. Study Conclusion

The experiment will terminate when the final participant has completed their treatment and all data has been analyzed.

e. Data Safety Monitoring Plan (DSMC)

i. Data and/or events subject to review

Adverse events, protocol deviations, aggregate data will all be frequently reviewed by the Study PI and Protocol Director (PD).

ii. Person(s) responsible for Data and Safety Monitoring

The Principal Investigator and Protocol Director

iii. Frequency of DSMB meetings

N/A

iv. Specific triggers or stopping rules

If there is evidence of significant risk to the participants such as multiple seizure events or worsening of psychiatric state in more than 20% of the participants.

v. DSMB Reporting

N/A

vi. Will the Protocol Director be the only monitoring entity? (Y/N)

Yes

vii. Will a board, committee, or safety monitor be responsible for study monitoring?
(Y/N)

No

f. Risks to Special Populations

N/A

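### Objective 1 aims to determine equivalence to traditional rTMS in unipolar depression, but the design is one open-label group of 30 bipolar patients with no rTMS or unipolar group

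*Protocol*

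**What the plan says.** Protocol section 1b, Objective 1, asks whether bilateral accelerated iTBS can rapidly reduce depressive symptoms in bipolar depression to a degree "that is equivalent to the efficacy of the traditional repetitive transcranial magnetic stimulation (rTMS) paradigm for unipolar depression". The objective is phrased as something the study will determine.

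The design is fixed elsewhere in the protocol:

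- **Size and type** (section 2a): "We will recruit a total of 30 outpatient participants for an open label pilot study".
- **Treatment** (section 5, Planned Enrollment): all 30 are planned for one treatment, "using bilateral intermittent theta burst stimulation (iTBS) over the left dorsolateral prefrontal cortex (LDLPFC) and right dorsolateral prefrontal cortex (RDLPFC"). Section 6c allows a departure within this group when mania ratings rise: "stimulation will be switched to all right sided treatment".
- **Population** (section 5, Inclusion Criteria): patients "with a primary diagnosis of bipolar I or II disorder in a current major depressive episode". No unipolar patient can enter.
- **Traditional rTMS**: it appears in the background (section 3a), as an alternative to taking part (section 2e) and as an option after the study (section 2f). It is never a study treatment.

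The visit schedule in section 2a has one cell reading only randomization, with no arms, ratio or comparator there or elsewhere. The recruitment section says data will be shared with two other studies, but describes no control group drawn from them.

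**The concern.** A claim of equivalence is a claim about a comparison, and this study contains only one side of it. Patients on traditional rTMS with unipolar depression would have to come from other studies, run at other times on other people.

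Treatment package and diagnosis both differ from the reference, but that is the contrast the objective names. The difficulty is everything else that differs between studies: how patients were selected, where they were treated, who rated them and how, and what they expected from an open-label treatment. These are mixed into the observed contrast, and a single group cannot take them out.

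If the objective stands, a result close to published rTMS results could be reported as demonstrated equivalence when part of it reflects differences between studies.

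**Working it through.** **1. Objective against design**

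| Needed for the equivalence claim | What the protocol provides |
|---|---|
| Patients on traditional rTMS | None in the study |
| Patients with unipolar depression | Not eligible |
| Concurrent or randomised comparison | None; one undefined schedule cell |
| Comparable selection and rating | Open-label ratings and a selective sample: stable mood stabiliser for 6 weeks, no rapid cycling, no hospitalisation within 6 months for suicidality, depression severity or hypomania, no active suicidal ideation |

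The finding follows from this table alone. A benchmark, margin and endpoint may be set in an analysis plan, so their absence is not counted here. The figure of 30 comes with no derivation, so there is nothing to reproduce.

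**2. Illustration: what between-study bias does**

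The only input from the protocol is n = 30. The protocol gives no traditional rTMS response rate, so these are assumptions:

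- a binary response and a benchmark p0 of 40%, 50% or 60%, known without error;
- a margin of ±20 points, with equivalence declared if the 90% confidence interval lies wholly inside p0 ± 0.20;
- a true response rate of p0 − 0.20, the edge of non-equivalence;
- between-study differences that add a bias b to the observed rate.

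The responder count is X ~ Binomial(n, p0 − 0.20 + b). The error is the sum of P(X = x) over every x whose interval fits inside the margin. At p0 = 50% and n = 30 the qualifying counts are 14, 15 and 16. With b = 0.10 the observed-scale rate is 0.40, and P(14 ≤ X ≤ 16) = 23.7%.

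The ranges below cover the three benchmarks and two interval methods (Clopper-Pearson and Wilson):

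| Bias b | False equivalence, n = 30 | False equivalence, n = 120 |
|---|---|---|
| 0 | 2.5–6.0% | about 4–6% |
| 10 points | 23.0–37.1% | 67.6–81.4% |
| 20 points | 41.5–53.8% | 99.5–99.7% |

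Without bias the error stays near its nominal level. With bias it grows with the sample, because more patients make a biased comparison more precise. In the last row the bias exactly cancels the true deficit, so the n = 30 entry equals the power when the true rate is at the benchmark.

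**3. Precision at n = 30 (a secondary matter)**

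- The exact 95% interval for 15 of 30 responders is 31.3–68.7%.
- With the true rate at the benchmark and no bias, power for equivalence is 0% at ±10 points and 41.5–53.8% at ±20 points.

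**4. The same on a continuous scale**

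- The 95% half-width for mean change is t(0.975, 29)/√30 = 2.045/5.477 = 0.373 SD. For an assumed SD of 8–12 points this is 3.0–4.5 points.
- Two one-sided 5% tests with 29 degrees of freedom reach 80% power at a margin of 0.547 SD, or 4.4–6.6 points.
- With the true mean at the lower margin, false equivalence is 5.0%, 13.3%, 28.2% and 47.9% for a bias of 0, 0.1, 0.2 and 0.3 SD.

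**The case against.** The strongest reply is that the word is used loosely. The protocol calls the study a pilot and states no equivalence hypothesis, test or decision rule. Objectives 2 and 3 use similarly informal comparative language. On that reading Objective 1 asks only whether the benefit is of the same order as that of rTMS in unipolar depression. No objective is named primary, and no sample size, stopping rule or treatment step depends on the clause. This limits the consequence but does not remove the mismatch: an aim to determine equivalence states a conclusion, and if rough similarity was meant, saying so costs nothing.

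A second reply is that a single group can be judged against an external benchmark, with sensitivity analyses for comparability. That is fair as far as it goes. Such an analysis can show that a result lies near a benchmark. It reaches equivalence only by assuming that between-study bias is negligible or of known size, which this study cannot check.

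The third reply concerns the numbers. Benchmark, margin, bias and the direction of the true difference are all assumed. The protocol's own earlier data point upward: about 90% response, and remission in 5 of 5 bipolar patients. A result near 90% would fail a ±20-point equivalence rule around 40–60% on the high side. This is correct, so the figures show how the error behaves and do not predict what will happen here. The precision figures in steps 3 and 4 are also a separate issue that, unlike bias, more patients would improve.

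**Conclusion.** The concern holds. Objective 1 promises a conclusion that one open-label group of 30 bipolar patients cannot deliver, and no analysis plan can supply the missing groups. This rests on the protocol's own text and needs no numerical assumption.

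The size of the possible error cannot be known from the document. Under the assumptions in step 2, a 10-point between-study bias raises the chance of wrongly declaring equivalence from 2.5–6% to 23–37% at 30 patients, and enlarging the study makes it worse. The point should be fixed. It affects what the study may claim, not its conduct.

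**What to change.** Delete the equivalence clause and restate Objective 1 as estimation, for example:

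> To estimate, with a 95% confidence interval, the change in depressive symptoms from baseline (Visit 2) to immediate post-treatment (Visit 8) on [MADRS-C or HAMD-17; sponsor to choose one] after bilateral accelerated iTBS in bipolar depression, and the response proportion, as defined by the sponsor, with its 95% confidence interval.

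Then add:

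> Any comparison with published rTMS results in unipolar depression is non-concurrent and descriptive only.

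Both scales are already scheduled. The baseline cell of the visit schedule lists "MADRS-C HAMD-17", and the Visit 8 column lists the same two scales across its two rows. If the scale, time point and response definition are set in an analysis plan, the objective should match them. The sponsor's question survives as a labelled external comparison.

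The cost is a protocol wording change and a more modest claim. It adds no patients, visits or procedures.

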Our recent pilot study utilized prior evidence to further enhance the propensity of antidepressant response to iTBS by modifying parameters in pulse spacing, dosage and treatment target location (Cazzoli et al., 2012; Fox et al., 2012; Gamboa, Antal, Moliaidze, & Paulus, 2010; Noh, Fuggetta, Manganotti, & Fiaschi, 2012; Nyffeler, Cazzoli, Hess, & Muri, 2009). Applied in a small pilot sample of individuals with unipolar (n=20) and bipolar (n=5) TRD, the use of an accelerated iTBS paradigm yielded approximately 90% response and remission rates in depressive symptoms, in both unipolar and bipolar TRD patients (Cole et al., Manuscript in preparation). Of the 5 bipolar TRD patients, all met depression remission criteria within 5 days of treatment, with no hypomania/mania conversion observed during treatment or at follow-up. This study aims to further explore the use of an adapted accelerated iTBS protocol for bipolar TRD.

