13. IQ<70
14. Parkinsonism or other movement d/o determined by PI to interfere with treatment

15. Any other indication the PI feels would comprise data.
16. No access to clinical rTMS after discharge
17. Active suicidal ideation
18. A diagnosis of obsessive-compulsive disorder (OCD)
19. Any history of psycho surgery for depression
20. Any history of myocardial infarction, CABG, CHF, or other cardiac history
21. The presence or diagnosis of prominent anxiety disorder, personality disorder or dysthymia
22. History of intractable migraine
23. Mania in the past year, and/or hypomania in the past 6 months.

j. Screening Procedures

Participants will be seen in the bipolar research clinic for treatment consultation. At that time, standard of care treatments will be offered as well as this protocol. The bipolar research clinic screening database will be used to identify potential participants, as for all bipolar research clinic studies.

k. Participation in Multiple Protocols

We will not enroll participants that are involved in any other treatment trial. We will coordinate with any ongoing biomarker studies to ensure that the treatment follows the biomarker study.

l. Payments to Participants

There will be payment given for the Probabilistic Reward Task. The Probabilistic Task is a neurocognitive assessment to test motivation in depressed patients. Each participant will be paid a total of \$72 for participation in the Probabilistic Reward Task at each of the 3 defined time points above: Baseline visit, Immediate post-treatment follow-up and 1 month-visit (roughly ~\$24/visit for a total of \$72 across all 3 visits). Anhedonia, defined as the lack of reactivity to pleasurable stimuli, is a common symptom in depression. The goal of this task is to determine the degree of blunted reward-response in depressed participants.

m. Costs to Participants

No cost to the participant.

n. Planned Duration of the Study

The estimated duration for screening activities is one day.

The estimated duration for active participation is a maximum of 10 days. The active study period includes pre-measurements, 5 stimulation days, and immediate post and 1-month post-measurements). Following the 1-month follow-up, we will continue following patients biweekly for up to 6 months since their last aiTBS treatment. These follow-ups will be done via online self-reports until participants are no longer responders.

The estimated duration for analysis of participant data is 6 months.

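### Objective 2 asks about connectivity change in responders only, so in a single-arm trial it cannot show that the change goes with improvement

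*Protocol*

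**What the plan says.** Protocol section 1b sets three objectives. The second is "To determine if responders to this protocol will have a similar change in functional connectivity" between the left DLPFC and the sgACC after treatment. It does not mention non-responders and does not say what the change should be similar to. The third concerns "potential predictors of antidepressant treatment response and durability (time to relapse) in bipolar depression".

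Section 2a gives the design: "We will recruit a total of 30 outpatient participants for an open label pilot study". No control arm is described. The visit schedule in the same section lists "Resting state fMRI connectivity" at baseline and at the immediate post-treatment visit, and MADRS-C and HAMD-17 at both visits. None of these is limited to responders.

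On response rates, section 1a says the pilot "has shown a 90% antidepressant response in individuals with treatment resistant MDD, over the course of only 5 days". Section 3a says the paradigm "yielded approximately 90% response and remission rates in depressive symptoms, in both unipolar and bipolar TRD patients", with 20 unipolar and 5 bipolar patients, and adds: "Of the 5 bipolar TRD patients, all met depression remission criteria within 5 days of treatment". No response rate is stated as an assumption for this trial.

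The protocol uses responder status as a category in section 5n, for the follow-up of up to 6 months: "These follow-ups will be done via online self-reports until participants are no longer responders". It gives no cut-off for response and names no test of responders against non-responders.

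**The concern.** Objective 2 is a mechanistic question. The reader wants to know whether connectivity changes because, or at least when, patients improve. In a single-arm study, the only internal evidence on this is variation between participants: do those who improve more also change more? Restricting the question to responders removes the low end of that variation. What remains is a before-after change in a group chosen for having improved. Time, a second scan, regression to the mean or the stimulation itself could each produce it.

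If the objective is followed as written, a responder-only change may be reported as a mechanism with no evidence that it relates to benefit. An analysis plan can choose the test, but it cannot bring in non-responders and still answer the objective as worded.

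A lesser, conditional concern attaches to Objective 3. If treatment response were taken as yes/no, a high response rate would leave few non-responders and much less information about predictors.

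**Working it through.** **1. Objective 2: what each analysis can separate.** No arithmetic is needed.

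- *Responders only, post minus baseline.* Suppose time or repeat scanning shifts connectivity by the same amount in everyone. The mean change in responders then contains that shift in full, and nothing in the analysis removes it.
- *All participants, connectivity change against symptom change.* A shift common to everyone goes into the intercept. The slope or correlation reflects only whether larger symptom change goes with larger connectivity change.

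The response rate does not enter this argument.

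**2. Precision of the all-participant analysis.** The input is n = 30 (section 2a), assuming all have both scans. Two-sided 5% and 80% power are my assumptions, because the protocol gives no design inputs for this objective.

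- Detectable correlation by Fisher's z: tanh[(1.960 + 0.842)/√(30 − 3)] = tanh(0.539) = 0.49.
- Illustrative 95% CI at an observed correlation of 0.5: 0.549 ± 1.960/√27 = 0.549 ± 0.377 on the z scale, or 0.17 to 0.73.

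The interval is wide but informative for a pilot.

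**3. Objective 3: information kept if response were dichotomised.** Let p be the response rate. Assume a normally distributed outcome, cut at the point that gives p. The efficiency relative to the continuous outcome is φ(z_p)²/[p(1 − p)]. Expected non-responders are 30(1 − p).

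| p | Expected non-responders | Calculation | Information kept | Equivalent n of 30 |
|---|---|---|---|---|
| 0.90 | 3 | 0.1755²/0.09 | 34% | 10.3 |
| 0.80 | 6 | 0.2800²/0.16 | 49% | 14.7 |
| 0.70 | 9 | 0.3477²/0.21 | 58% | 17.3 |
| 0.50 | 15 | 0.3989²/0.25 | 64% | 19.1 |

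At p = 0.90, the chance of 3 or fewer non-responders is 65%, and the chance of none is 0.9³⁰ = 4.2%.

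**4. The same loss as power for one continuous predictor.** This comes from 20,000 simulated trials per setting (n = 30, bivariate normal, two-sided 5%, samples without both groups counted as no detection). The true correlations are assumptions.

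- Correlation 0.5: about 83% with continuous change. With responder status, 34% at p = 0.90, 49% at 0.80, 56% at 0.70 and 62% at 0.50.
- Correlation 0.4: about 61% with continuous change, against 23% at p = 0.90.

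**5. How firm is 90%?** It is a pilot figure. The bipolar evidence is 5 of 5 remitted, with exact lower 95% limit 0.025^(1/5) = 0.48. The interval of 48% to 100% covers every row of the table.

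**The case against.** The strongest reply is that most of the arithmetic describes an analysis the protocol does not specify. Much of that reply stands.

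- *Objective 3 is not fixed as binary.* Treatment response can be read as continuous symptom change. No cut-off or group test is given, and a statistical analysis plan, not shown here, could settle it without departing from the objective. Steps 3 and 4 therefore show what one choice would cost. They do not show an error in the protocol.
- *90% is not this trial's assumption.* A reader might infer that the protocol expects about 3 non-responders. It only reports pilot results.
- *Objective 2 does not discard most of the data.* A reader might infer this from the table. At 90% response, a within-responder analysis keeps about 27 of 30 participants; its fault is the missing contrast. A 27 against 3 comparison detects only a standardised difference of about 1.77 with 80% power, but Objective 2 proposes no such comparison, so that figure does not measure its defect.
- *Durability properly concerns responders.* Time to relapse has meaning only after response, and a high response rate helps it. Calling both objectives close to unanswerable would go too far.
- *Similar* plausibly refers to the earlier studies on which section 2a models the design. An external reference is normal in a single-arm pilot.
- *The power figures depend on the model.* If most patients remit, percent change may bunch near its ceiling and 83% would be optimistic.

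None of this answers the point about Objective 2. Its wording names responders, and no later choice of test supplies the missing contrast.

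**Conclusion.** The point holds for Objective 2 at any response rate: as worded, it selects on outcome and cannot link connectivity change to improvement. That conclusion rests on the wording and the single-arm design, not on a numerical assumption.

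For the response part of Objective 3, the point is a recommendation to make the outcome explicit. Dichotomising would lose between 36% (at 50% response) and 66% (at 90%) of the information, assuming a normal outcome. The loss exceeds half only at response rates of about 80% or more, so a general statement that most of the information is lost is not supported. The time-to-relapse part needs no change.

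This is a wording change worth making to exploratory aims of a pilot; it does not threaten the trial as a whole. Even the all-participant association would not prove mechanism without a control arm. It would remove the explanations that act equally on everyone.

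**What to change.** - **Objective 2:** restate it for all treated participants with pre- and post-treatment scans. Estimate the association between change in DLPFC-sgACC connectivity and continuous change in one named clinician-rated scale, MADRS-C or HAMD-17, with its 95% CI. Keep the mean change in responders as a descriptive summary. State that similarity is a descriptive comparison with the earlier studies.
- **Objective 3, response part:** name continuous symptom change as the outcome, with responder status descriptive.
- **Objective 3, durability part:** leave time to relapse on responders.

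The cost is wording only, because the scans and scales are already scheduled. The small downside is that results are expressed per unit of improvement instead of as a statement about responders, which some clinical readers find easier. The descriptive responder summary covers that need.
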